7.4 Sensitivity Analyses of the Primary Outcome

Additional analyses of the primary outcome may include, but are not limited to:

1. A replication of the primary analysis with stratification by recruitment source (ARIC vs de novo). An interaction between treatment assignment and recruitment source will be tested relative to $p < 0.10$.
2. An analysis of subjective, self-reported hours of hearing aid use including differences between the use of hearing aids and hearing assistive technologies.
3. An analysis restricted to participants who wore the same type of hearing aid.
4. Exploration of the impact on the primary analysis by further adjustment for additional explanatory variables.

7.5 Secondary Outcomes

Secondary outcomes that will be examined include:

1. Treatment satisfaction, as assessed by a single item from the International Outcome Inventory – Comprehensive Hearing Intervention (IOI-CHI). The IOI-CHI is an interviewer-administered scale that consists of 6 items where participants self-report satisfaction with the hearing intervention using a 5-point Likert scale. A higher score indicates a more favorable outcome.
2. Ability to hear for the primary communication goal as assessed by a single item from the Client-Oriented Scale of Improvement (COSI) goals achievement questionnaire. COSI goals are rated using a 5-point Likert scale. A higher score indicates the participant is able to hear more of the time.
3. Hearing-specific quality of life, as assessed by the Hearing Handicap Inventory for the Elderly Screening Version (HHIE-S) questionnaire. The HHIE-S is an interviewer administered questionnaire that consists of 10 items. Participants rate whether hearing loss affects them in

different situations (yes, sometimes, or no). The total score is the sum of all responses and ranges from 0 to 40, with higher scores indicating greater hearing issues.

For continuous secondary outcomes, groups will be compared for differences at the one-year follow-up using the same analytic approach specified for the primary outcome. For binary secondary outcomes, either logistic regression or Poisson regression with robust error variance will be employed depending on whether the outcome is rare or common. For categorical outcomes, either ordinal or multinomial logistic regression models will be utilized depending on the nature of the measure and empirical tests of the proportional odds assumption.

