7.1 Schedule of activities

Table 1 details which data will be gathered and when. Data collection visits may be split across multiple days or multiple settings (clinic visits, home visits, telephone contacts, or video calls) to meet the needs of our participants. Some items related to exploratory outcomes might be dropped based upon participant burden, scientific considerations, or available resources.

Table 1. Schedule of Activities and Evaluations

Follow-up visit	Baseline	Random- ization visit	Ini	health Sestial Telehenized HHC	alth	6-month	Year 1 (12mo)	Initia	nealth Ses al Convent ized HHC B	ional	18- month	Year 2 (24mo)
Visit relative to parent	Yr 3					Yr 3.5	Yr 4				Yr 4.5	Yr 5
ACHIEVE Trial (approx.)						(42mo)	(48mo)				(54mo)	(60mo)
Randomization												
Informed consent		Х										
Randomization		Х										
GrandPad distribution		Х										
Hearing Intervention	L	l	ı			L	L		l			
GrandPad instructions for telehealth			Х					Х				
Intervention check-up	Х											
HIFU Intervention check-up		Х	Xc	X	Х	Х	Х	Xc	Х	Х	Χ	Х
International Outcome Inventory for Comprehensive Hearing Intervention	Х					Х	Х				Х	Х
Client-Oriented Scale of Improvement (COSI) goal setting		х										
COSI goals achievement				Х	Х	Х	Х		Х	Х	Χ	Χ
Audiometry		•		•	•			•	•			
Air conduction audiometry	Х						Х					Х
Bone conduction audiometry	Х						Xd					Xd
Tympanometry	Х						Х					Х
Word Recognition in Quiet	Х						Х					Х
Quick Speech in Noise (unaided)	Х						Х					Х
Social Functioning and Qua	lity of Lif	e Outcon	nes									
CES-D Scale	Х					Х	Х					Х
Hearing Handicap Inventory for the Elderly - Screening Version	х						Х					Х
RAND-36 Health Survey	Х						Х					Х
Cohen Social Network Index	Х						Х					Х
UCLA Loneliness Scale	Х						Х					Х
Hospitalizations	Х					Х	Х				Х	Х
Qualifying (S)AE assessment	Х					Х	Х				Х	Х

Follow-up visit	Baseline	Random- ization visit	Init	nealth Ses ial Telehe ized HHC	alth	6-month	Year 1 (12mo)	Initia Random			18- month	Year 2 (24mo)
		VISIL	A ^a	В	С			A ^b	В	С		
Covariates												
Health history	X						Χ					Х
Neurologic history	Х						Х					X
Anthropometry	Х						Χ					Х
Seated blood pressure	Х						Х					Х
COVID impact questionnaire	Χ					Х	Χ				Х	Х
Telehealth acceptance pre- intervention (TAP)		Х					Xe					
Telehealth acceptance						X ^f	X ^f				V	Х
follow-up (TAF)						Χ'	X'				X	X
Other Data Collection												
Baecke activity questionnaire	Χ						Χ					Х
Accelerometry	Χ						Χ					Х

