11.2 Analytic approach

The final statistical analysis plan was finalized in discussions between the study investigators and coordinating center.

The comparison for all primary analyses is randomization to the telehealth HHC vs. conventional clinic-based HHC delivery model under the intention-to-treat paradigm, analyzing individuals according to their random allocation, irrespective of the treatment received.

Consistent with best practices in clinical trials, we will assess the comparability of the randomized groups with respect to known confounders, such as recruitment source, site, level of hearing impairment, Quick Speech in Noise score, self-reported acceptance of telehealth at baseline, self-reported and objectively measured baseline hours of hearing aid use, self-reported baseline hours of hearing assistive technologies use, the number of days hearing log data was measured prior to randomization, and the number of visits prior to randomization at which a participant provided hearing logging data.⁴⁸ These variables will be considered as covariates in all models. If there is an imbalance between randomized treatment assignment, we may adjust for relevant confounders as well as explore the use of a prespecified inverse probability of treatment weight or a precise, locally efficient, augmented, simple estimator.^{49,50} A logistic regression model will be used to model the probability of attrition according to the confounders described above plus age, sex, and applicable interactions. Inverse probability of attrition weights will be calculated and either included in the model for the primary outcome directly or cross-multiplied with inverse probability of treatment weights.

We will use a weighted regression model with an identity link to compare average daily hours of hearing aid use at 1-year post-randomization between participants assigned to the telehealth HHC or conventional HHC. To account for the non-normal distribution of the outcome, confidence intervals and p-values will be obtained using the bias corrected and accelerated bootstrap resampling procedure with 10,000 replicates.

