7.3 Primary Analysis

We will use a weighted regression model with an identity link to compare average daily hours of hearing aid use at one-year post-randomization between participants assigned to the telehealth HHC or conventional HHC. To account for the non-normal distribution of the outcome, confidence intervals and p-values will be obtained using a bias corrected and accelerated bootstrap resampling procedure with 10,000 replicates. Consistent with best practices in clinical trials, we will assess the comparability of the randomized groups with respect to potential confounders [13], such as recruitment source, site, level of hearing impairment, Quick Speech in Noise score, self-reported acceptance of telehealth at baseline, self-reported and objectively measured baseline hours of hearing aid use, self-reported baseline hours of hearing assistive technologies use, the number of days hearing log data was measured prior to randomization, and the number of visits prior to randomization at which a participant provided hearing logging data. If there is an imbalance between randomized treatment assignment we may adjust for relevant confounders as well as explore the use of a prespecified inverse probability of treatment weight [14] or a precise, locally efficient, augmented, simple estimator [15]. A logistic regression model will be used to model the probability of attrition according to the confounders described above plus age, sex, and applicable interactions. Inverse probability of attrition weights will be calculated and either included in the model for the primary outcome directly or cross-multiplied with inverse probability of treatment weights.

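### Adjustment of Year 1 HHIE-S and IOI-CHI satisfaction for their own baseline values is not prespecified, although both baselines are collected

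*SAP*

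**What the plan says.** - **Secondary comparison.** SAP 7.5 states for continuous secondary outcomes that "groups will be compared for differences at the one-year follow-up using the same analytic approach specified for the primary outcome". For categorical outcomes it names ordinal or multinomial logistic regression, without covariates or weights. It does not say which route the 5-point IOI-CHI and COSI items take.
- **Covariates carried over.** SAP 7.3 says "we will assess the comparability of the randomized groups with respect to potential confounders [13], such as recruitment source, site, level of hearing impairment", and continues with further examples. One of these is "self-reported and objectively measured baseline hours of hearing aid use", which contains the primary outcome's own baseline. Baseline HHIE-S and baseline IOI-CHI are not mentioned. Protocol 11.2 gives the same list.
- **Status of adjustment.** SAP 7.3: "If there is an imbalance between randomized treatment assignment we may adjust for relevant confounders". Protocol 11.2: "These variables will be considered as covariates in all models". Neither wording commits to adjustment.
- **Attrition weights.** SAP 7.3 and Protocol 11.2 build the attrition model from the same list plus age, sex and interactions, and attach the weights to the primary outcome model.
- **Data available.** In Protocol Table 1 (section 7.1), the row "Hearing Handicap Inventory for the Elderly - Screening Version" is marked at baseline, Year 1 and Year 2. The row "International Outcome Inventory for Comprehensive Hearing Intervention" is marked at baseline, 6 months, Year 1, 18 months and Year 2. COSI goals achievement is rated only after randomization. The parent trial's Year 3 visit serves as baseline (Protocol section 7).

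**The concern.** A participant's own earlier score is the natural prognostic covariate for a repeated scale. The plan recognises this for hours of use, but when the approach is carried over to the secondary outcomes, the named baseline remains baseline hours. Nothing tells the analyst to use baseline HHIE-S for HHIE-S, or the baseline satisfaction item for satisfaction.

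Two things are at stake. One is precision on two of the three secondary outcomes, which share a Hochberg procedure (SAP 7.7). The other is prespecification: with an open list and adjustment triggered by observed imbalance, the covariates of these models could be settled after the data are seen.

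**Working it through.** **The plan's own figures.** SAP section 5 assumes 340 randomized and 5% loss in a year: 340 × 0.95 = 323, against 322 stated, which agrees within rounding. It then gives a detectable difference of 1.5 hours for the primary outcome. No SD is stated, so this cannot be reproduced; with the formula below it implies an SD of 1.5 / 0.3123 = 4.80 hours. Neither document gives a power figure, SD or baseline-to-Year-1 correlation for HHIE-S or IOI-CHI.

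**Inputs.** N = 322 (SAP 5), 1:1 allocation (Protocol section 8), 80% power and alpha 0.05 (SAP 5), taken as two-sided. The baseline-to-Year-1 correlation r is an assumption. Results are in SD units, so the different HHIE-S ranges in the two documents (0 to 20 in Protocol section 3, 0 to 40 in SAP 7.5) do not affect them.

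**Step 1: no covariates.** Detectable difference = (1.960 + 0.842) × √(4/322) = 2.802 × 0.1115 = 0.312 SD.

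**Step 2: own baseline as covariate.** Residual variance is multiplied by 1 − r², so the standard error and the detectable difference are multiplied by √(1 − r²).

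| Assumed r | Residual variance falls by | SE falls by | Detectable difference (SD) | Power at 0.312 SD | 322 act like |
|---|---|---|---|---|---|
| none | – | – | 0.312 | 80% | 322 |
| 0.3 | 9% | 4.6% | 0.298 | 83.6% | 354 |
| 0.5 | 25% | 13.4% | 0.270 | 89.9% | 429 |
| 0.7 | 49% | 28.6% | 0.223 | 97.5% | 631 |

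The last column is 322 / (1 − r²).

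**Step 3: strictest Hochberg level.** At 0.05/3 the starting value is 0.361 SD. Multiplying by the same factors gives 0.344, 0.312 and 0.258 SD for r = 0.3, 0.5 and 0.7.

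**Step 4: if the listed covariates are already in the model.** Suppose, again as an assumption, that their combined score correlates a = 0.4 with both the baseline and the Year 1 score. They alone bring 0.312 down to 0.312 × √(1 − 0.16) = 0.286 SD. The remaining partial correlation of own baseline with outcome is (r − a²)/(1 − a²):

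- r = 0.3: 0.14/0.84 = 0.167, a further SE reduction of 1.4%
- r = 0.5: 0.34/0.84 = 0.405, a further 8.6%
- r = 0.7: 0.54/0.84 = 0.643, a further 23.4%

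**Scope.** These figures apply to HHIE-S, and to the satisfaction item only if it is analysed as continuous. In an ordinal model a prognostic baseline also raises power, but the amount depends on the split across the five categories, which the documents do not give.

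**The case against.** The strongest reply is that the plan already permits this adjustment. The covariates are introduced as examples, relevant confounders may be added on imbalance, and the approach for hours of use includes the baseline of hours of use. By analogy, using the same approach for HHIE-S could mean using baseline HHIE-S. That stands: a reader might infer that the two outcomes will be compared without their baseline values, and the documents do not say so. They leave the choice open. An open choice does not answer the point about prespecification, and a trigger based on observed imbalance is a poor rule for a covariate whose value lies in its prognostic strength.

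The second reply is that the gain may be modest. SAP section 4 puts randomization up to 9 months after the baseline visit, and later for some participants at one site, so baseline can precede Year 1 by 9 + 12 = 21 months or more. Satisfaction is a single 5-point item. Both features could lower r, and at r = 0.3 the gain is small. That also stands: a claim that much of the available precision is lost holds only if r is about 0.5 or higher.

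Three further inferences are not supported:

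- **Bias.** Chance baseline differences are random error already reflected in the standard error. Randomization protects the unadjusted comparison.
- **Unweighted ordinal models for the 5-point items.** SAP 7.5 does not assign them to a route. If they are continuous they inherit the weights; if categorical, the text is silent.
- **A fixed hurdle of 0.017.** Under Hochberg that level applies only when the two larger p-values have missed 0.05 and 0.025.

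**Conclusion.** The point holds as a gap in prespecification with a cost in precision. Neither SAP 7.5 nor Protocol 11.2 commits to adjusting Year 1 HHIE-S or IOI-CHI satisfaction for its own baseline, although both baselines are scheduled. Against a model with no covariates, the residual variance given up is 9% to 49% for r between 0.3 and 0.7. It is less if the listed covariates are used and already explain part of the outcome. The size rests wholly on r, which the documents do not give; the absence of a commitment does not. Adjustment for a pre-randomization score is valid whatever r turns out to be, so the case for fixing it does not depend on r being high.

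**What to change.** In SAP 7.5, with Protocol 11.2 aligned, state the following before the Year 1 data are unblinded:

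1. The HHIE-S model always includes the baseline HHIE-S total, and the satisfaction model always includes the baseline satisfaction item, regardless of observed balance.
2. That baseline value is added to the attrition model for the same outcome.
3. Whether the 5-point items are analysed as continuous or ordinal, with the same attrition weights under either route.
4. COSI, which has no baseline rating, keeps the common covariates.
5. A simple rule for missing baseline scores, for example imputing the mean of both arms combined.

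No data collection changes. The cost is SAP wording and a matching Protocol amendment, which needs IRB approval under Protocol section 1. There is one small statistical cost: in an ordinal logistic model the adjusted odds ratio is conditional on baseline and differs in meaning from the unadjusted one, so the report should say which is presented.

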7.7 Adjustment for Multiple Comparisons

Statistical significance for the primary outcome will be defined as $p < 0.05$. Secondary outcomes will be evaluated for statistical significance with a Hochberg modification to the Bonferroni adjustment, in which the p-values of the five outcomes will be ordered. The largest p-value will be compared relative to $p < 0.05$,

and if met, all parameters will be considered significant. If not, then the second largest p-value will be assessed relative to $p < 0.05/2 = 0.025$, and if met then it and all other parameters will be considered significant, and so on for the third p-value at $0.05/3=0.017$.

8. Software and Statistical Programming

Tabulations and statistical analyses will be performed using SAS® Version 9 (or later). All programming will be done by the ACHIEVE DCC which is housed in the Collaborative Studies Coordinating Center (CSCC) at the University of North Carolina at Chapel Hill. Standard CSCC statistical computing procedures will be followed. That is, research staff will submit a written statistical computing request to the statistical programming staff. A computing request number will be assigned to the request and information about the request entered into a database. A statistical programmer will then be assigned to undertake the request. Statisticians will review the programs and output. If necessary, changes will be requested in writing. After the programming has been completed to the satisfaction of the staff, all materials will be archived under the request number. Archived materials will include the original computing request, any subsequent changes, the SAS® code as well as any output, including log and list files and datasets created in the request.

9. References

- [1] American Speech Language Hearing Association , "Preferred Practice Patterns for the Profession of Audiolog," *Rockville, MD*, 2006.
- [2] Audiology Australia, "Audiology Australia Professional Practice Standards – Part B: Clinical Standardsle," *Forest Hill, Victoria*, 2013.
- [3] British Society of Audiology, "Practice Guidance: Common Principles of Rehabilitation for Adults in Audiology Services," *Bathgate, UK*, 2016.
- [4] J. H.-Y. Ng and A. Y. Loke, "Determinants of hearing-aid adoption and use among the elderly: A systematic review," *Int J Audiol*, vol. doi: 10.3109/14992027.2014.966922, pp. 1-10, 2015; 2027 (April 2014).

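### Choosing between an ordinal and a multinomial model by a proportional-odds test on the trial data could raise the type I error of the two 5-point secondary items from 5% to as much as about 8%

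*SAP*

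**What the plan says.** SAP 7.5 lists three secondary outcomes. Two are single ordered items. For the IOI-CHI, "participants self-report satisfaction with the hearing intervention using a 5-point Likert scale"; for the COSI, "COSI goals are rated using a 5-point Likert scale". The third is the HHIE-S sum score.

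The section then gives analysis rules by type of outcome, without assigning the listed outcomes to types:

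- Continuous: "For continuous secondary outcomes, groups will be compared for differences at the one-year follow-up using the same analytic approach specified for the primary outcome", that is, weighted linear regression with bootstrap inference.
- Binary: logistic or Poisson regression.
- Categorical: an ordinal or a multinomial logistic model, chosen "depending on the nature of the measure and empirical tests of the proportional odds assumption".

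Protocol 11.2 has the same rules. It adds that a list of about ten baseline variables will be considered as covariates in all models.

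SAP 7.7 then applies a family-wise rule: "Secondary outcomes will be evaluated for statistical significance with a Hochberg modification to the Bonferroni adjustment", with steps at 0.05, 0.025 and 0.017.

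Neither document states the type, level or scope of the proportional-odds test, or which p-value from a multinomial fit would go into Hochberg.

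**The concern.** The proportional-odds test is run on the same data as the treatment comparison, and its result helps decide which treatment test is used. With five categories, the ordinal model tests treatment on 1 df and the multinomial model on 4 df. The 4-df statistic contains the departure from proportional odds. When that departure is large by chance, the rule moves to the test that counts it as evidence of a treatment difference. When it is small, the rule stays with the 1-df test and keeps nearly all of that test's 5%. The two rejection routes add up to more than 5%.

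Hochberg relies on each p-value being valid at its nominal level, so the excess carries into the family-wise error for the secondary claims. The multinomial branch also ignores the ordering of the scale and gives four odds ratios instead of one. A significant global result would then not say in one number which delivery model did better.

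**Working it through.** **Inputs from the documents.** Five categories per item (SAP 7.5). Hochberg steps (SAP 7.7). 322 participants at one year (SAP 5), allocated 1:1 (protocol 8), so 161 per arm.

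**Assumptions, because the documents are silent.** Two-sided tests. Both items analysed as categorical. A rejected proportional-odds test leads to the 4-df global multinomial test. Level of the proportional-odds test 5%, with 1-20% as the range. Scope either treatment only or global over treatment and covariates.

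**1. The plan's own figures.** 0.05/1 = 0.05, 0.05/2 = 0.025 and 0.05/3 = 0.0167, as stated after rounding. 340 × 0.95 = 323 against the stated 322, an immaterial difference.

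**2. Decomposition.** Under the null, in large samples, the 4-df likelihood-ratio statistic is X1 + X3. X1 is chi-square on 1 df (treatment effect under proportional odds). X3 is an independent chi-square on 3 df (departure from it). The 5% critical values are 3.841 (1 df), 7.815 (3 df) and 9.488 (4 df).

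**3. Type I error of the two-step rule, treatment-only test at 5%.**

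P(reject) = P(X3 ≤ 7.815) × P(X1 > 3.841) + P(X3 > 7.815 and X1 + X3 > 9.488)

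= 0.95 × 0.05 + 0.0334 = 0.0475 + 0.0334 = **0.081**

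Once the proportional-odds test has rejected, the 4-df test also rejects with probability 0.0334/0.05 = 67%.

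**4. Other levels of the proportional-odds test (nominal 5% treatment test).**

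| Level | Ordinal branch | Multinomial branch | Total |
|---|---|---|---|
| 1% | 4.95% | 1.00% | 6.0% |
| 5% | 4.75% | 3.34% | 8.1% |
| 10% | 4.50% | 3.92% | 8.4% |
| 20% | 4.00% | 4.36% | 8.4% |

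At the later Hochberg steps, with the test at 5%, nominal 2.5% becomes 4.2% and nominal 1.67% becomes 2.9%.

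**5. Global test over treatment and covariates, all covariates satisfying proportional odds.** Each covariate df adds 3 df of noise to the test, so it responds less to the treatment departure. Type I error is 6.8% with 1 covariate df, 6.0% with 3, 5.8% with 5, 5.5% with 10 and 5.4% with 15.

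**6. Finite-sample check.** 100,000 simulated 2×5 tables per setting, 161 per arm, treatment-only test at 5%, category distributions assumed:

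- Categories of 5/10/20/35/30%: ordinal model alone 5.1%; two-step rule 8.2-8.5%, depending on the test variant.
- Very sparse low categories: two-step rule 6.5-8.9%; ordinal model alone 4.95-5.0%.

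Attrition weights and spouse pairs were not modelled.

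**7. Family-wise error.** Simulated Hochberg over three outcomes, two of them using the two-step rule with a treatment-only test at 5%. Three is the number listed in SAP 7.5; SAP 7.7 speaks of five.

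| Correlation | Fixed ordinal test | Two-step rule |
|---|---|---|
| 0 | 4.9% | 7.3% |
| 0.3 | 4.8% | 7.2% |
| 0.6 | 4.3% | 6.5% |

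**8. Power under proportional odds.** Take the noncentrality that gives the 1-df test 80% power (7.85). The two-step rule then rejects with probability 0.95 × 0.80 + 0.049 = 0.76 + 0.049 = 80.9%.

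**The case against.** The strongest reply is that the documents do not fix the rule that was calculated. The categorical sentence is generic: a binary rule stands beside it although none of the three outcomes is binary. SAP 7.6 averages IOI-CHI and COSI items as numeric scores. If the items are treated as continuous, no proportional-odds test applies to them. The choice also depends on the nature of the measure, which for an ordered scale favours the ordinal model, and nothing says that a rejected test forces the multinomial one. With a global, covariate-adjusted test, which protocol 11.2 makes plausible, the excess can be as small as half a point.

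All of this stands, and it is why the size must be given as a conditional range. It does not remove the point, because every categorical setting calculated is above 5%. The open choice between continuous, ordinal and multinomial analysis is itself a reason to name one model per item.

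Three stronger readings are tempting and not supported:

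- *The plan has an 8% error rate.* That figure needs a treatment-only test, at a level the documents do not state.
- *A p-value without direction breaks Hochberg.* Hochberg needs valid p-values, not directional ones. The documents also do not say that a global 4-df p-value would be used, and a multinomial fit does report signed category odds ratios.
- *The rule costs power, 80% falling to about 60%.* The 60% (59.5%) belongs to a 4-df test used always. Under proportional odds the two-step rule has about 81%.

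**Conclusion.** The point holds in conditional form. If the two 5-point items are analysed as categorical and a rejected proportional-odds test leads to a 4-df multinomial treatment test, type I error at nominal 5% rises to as much as about 8%. For an assumed treatment-only test it is 6.0%, 8.1% and 8.4% with that test at 1%, 5% and 10%. For a test that is global over treatment and covariates satisfying proportional odds, it is about 5.5-7%. If the items are analysed as continuous, the inflation does not arise.

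The lack of a single effect and direction in the multinomial branch limits interpretation; it is not a second source of error. The primary outcome is unaffected. This is a cheap improvement to the multiplicity-controlled secondary claims.

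**What to change.** In SAP 7.5 and protocol 11.2, name the 1-df cumulative-logit treatment test as the analysis of both 5-point items, whatever the proportional-odds test shows. Its p-value enters Hochberg, and the common odds ratio is the summary. Report category percentages by arm, with any partial-proportional-odds or multinomial fit as descriptive support only.

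The cost is about one sentence in each document. In the simulations at 161 per arm the fixed test held its level (4.95-5.1%). Its power at an assumed common odds ratio of 1.7 was 74.4%, against 75.5% for the two-step rule, which runs at a higher error rate. The small downside is that under strong non-proportionality the common odds ratio is an average effect; the category percentages would show this.
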